5.8.5. Analysis of 12-Lead ECG

For respective treatment period as defined for clinical laboratory measurements (Section 5.8.3), ECG parameters will be described through an overall interpretation of ECG status (e.g. normal, abnormal [clinically significant (Yes/No)]).

The count and percentage of patients with at least 1 abnormal post-baseline ECG during the respective TEAE period will be summarized according to the following baseline status categories:

- Normal/missing;
- Abnormal

Individual patient ECG measurements will be additionally evaluated by PCSV criteria, specifically identifying patients with at least one post-baseline measurement that meets the PCSV criteria within the TEAE period. The incidence of PCSVs at any time during the respective TEAE periods will be summarized regardless of the baseline level, and again according to the following baseline categories:

- Normal (according to PCSV criterion/criteria)/missing
- Abnormal according to PCSV criterion or criteria
- Patient listings of ECG measurements that meet PCSV criteria will be provided for the report appendix.
- administration in Part B for patients not entering into the Part C + 28 days.

5.8.6. Tanner Stages

For respective treatment period as defined for clinical laboratory measurements (Section 5.8.3), tanner stages (outcome categories of 1, 2, 3, 4, 5) will be summarized by patient frequency and percentage at baseline and each post-baseline visit. The change from baseline in tanner stage by visits will be assessed (No change in Tanner stage, change in Tanner stage ≥ 1).

5.8.7. Physical Exams

A list of patients with any clinically significant abnormality results will be generated.

5.9. Analysis of Other Variables

In general, for main study part (Part A or Part B), the summary of results for other variables for patients in the safety analysis set will be presented by each study part. No formal inferential testing will be performed. Summaries will be descriptive in nature.

For Part C, the summary of results for other variables for patients in the Part C safety analysis set will be presented for all patients and by main study part (Part A or Part B) in which patients are originally enrolled at the beginning of the study.

In addition, the analyses for other variables will be performed on the pooled data in the pooled safety analysis set. The summary of results will be presented by patient groups defined in Section 2.4.1.

All measurements, scheduled or unscheduled, fasting or not fasting, will be assigned to Global Analysis Windows (Appendix 10.2) in order to provide an assessment for all post-baseline visit.

Hs-CRP, HbA1c, HDL-C and cIMT parameters will be summarized for the number of patients with data, mean, SD, median, minimum, maximum, Q1 and Q3 by analysis visit during the treatment period. The medians (with Q1-Q3) will be plotted for hs-CRP. The means (+/-SE) will be plotted for HbA1c, HDL-C and cIMT. In addition, HbA1C will be summarized at each visit by diabetic status as recorded in the medical history e-CRF page (regardless of the ongoing status). Applying the PCSV criteria to HbA1c at any time during the TEAE period, the number of patients (and percentages) meeting the criteria will be summarized.

5.10. Analysis of Pharmacokinetic Variables

PK parameters for Part A may include, but are not limited to:

- C_{max}
- AUC_{last}

- AUC_{inf}
- CL
- V_{ss}
- MRT

PK parameters for Part B may include, but are not limited to:

- $C_{max,ss}$
- $C_{trough,ss}$

Descriptive statistics of concentrations of total evinacumab and total ANGPTL3 will be presented. For the determination of arithmetic means and descriptive statistics, individual concentration values below the LLOQ, will be set to zero. If geometric means are determined, individual concentrations values below the LLOQ will be imputed as LLOQ/2.

Plots of the mean concentrations (linear and log scales) will be presented by nominal sampling time. Plots of the individual concentrations (linear and log scales) will be presented by actual sampling time. In the linear-scaled plots, concentrations below the LLOQ will be set to zero; in the log-scaled plots, concentrations below the LLOQ will be imputed as LLOQ/2.

When appropriate, relationship between concentrations of evinacumab and LDL-C or other biomarkers may be evaluated descriptively.

5.11. Analysis of Immunogenicity Data

5.11.1. Analysis of ADA data

The ADA variables described in Section 4.11 will be summarized using descriptive statistics.

Immunogenicity will be characterized by ADA responses and titers observed in patients in the ADA analysis set. ADA response categories and titer categories are defined as follows:

Anti-drug antibody status and titer over the study duration may be classified as follows:

- ADA Negative, defined as ADA negative response in the assay at all timepoints, regardless of any missing samples.
- Pre-existing immunoreactivity, defined as a positive ADA assay response at baseline, with all post-first dose ADA results negative, or a positive assay response at baseline, with all post-first dose ADA assay responses less than 9-fold of baseline titer levels
- Treatment-emergent ADA response, defined as any post-first dose positive ADA assay response when the baseline results are negative
 - For Part B and Part C of the study, treatment-emergent ADA response will be further characterized as persistent, transient, or indeterminate:
 - Persistent Response – Treatment-emergent ADA positive response with 2 or more consecutive ADA positive sampling time points, separated by at least 16-week period (based on nominal sampling time), with no ADA negative samples in between, regardless of any missing samples.

- Indeterminate Response –Treatment-emergent ADA positive response with only the last collected sample positive in the ADA assay.
- Transient Response –Treatment-emergent ADA positive response that is not considered persistent or indeterminate.
- Treatment boosted ADA response, defined as any post-first dose positive ADA assay response that is 9-fold over baseline titer levels when baseline is positive in the ADA assay
- Maximum ADA Titer values
 - Low (titer <1,000)
 - Moderate ($1,000 \leq \text{titer} \leq 10,000$)
 - High (titer >10,000)

The following analysis will be provided:

- Number (n) and percent (%) of ADA-negative patients (pre-existing immunoreactivity or negative in the ADA assay at all time points) by treatment groups
- Number (n) and percent (%) of treatment-emergent ADA positive patients by treatment groups and ADA titer categories
- Number (n) and percent (%) of persistent treatment-emergent ADA positive patients
- Number (n) and percent (%) of indeterminate treatment-emergent ADA positive patients
- Number (n) and percent (%) of transient treatment-emergent ADA positive patients
- Number (n) and percent (%) of treatment-boosted ADA positive patients by treatment groups and ADA titer categories

Listing of all ADA titer levels will be provided for patients with pre-existing, treatment-emergent, treatment-boosted ADA response.

5.11.2. Analysis of Neutralizing Antibody (NAb) Data

The absolute occurrence (n) and percent of subjects/patients (%) with NAb status in the NAb analysis set will be provided by treatment groups.

5.11.3. Association of Immunogenicity with Exposure, Safety and Efficacy

5.11.3.1. Immunogenicity and Exposure

Potential association between immunogenicity and systemic exposure to REGN1500 will be explored. Plots of REGN1500 concentration may be provided for analyzing the potential impact of ADA response status, titer and NAb on the concentration time profiles.

5.11.3.2. Immunogenicity and Safety and Efficacy

Potential association between immunogenicity variables and safety may be explored with a primary focus on the following safety events during the TEAE period:

- Injection site reaction (serious or severe and lasting 24 hours or longer)
- Hypersensitivity (SMQ: Hypersensitivity [Narrow])
- Anaphylaxis (SMQ: Anaphylaxis [Narrow])

Potential association immunogenicity variables and efficacy endpoints may be explored (e.g. scatter plot or spaghetti plot).

The safety and efficacy analyses mentioned above will be conducted using the following categories:

- ADA positive patients, that is patients with treatment-emergent or treatment-boosted response.
- ADA negative patients, that is subjects/patients with pre-existing immunoreactivity or negative in the ADA assay at all time points.
- Patients with persistent treatment-emergent ADA response
- NAb positive patients, that is ADA positive patients who were positive in the NAb assay at any time point analyzed.
- Maximum post-baseline titer in treatment-emergent or treatment-boosted ADA positive patients:
 - Low (titer <1,000)
 - Moderate ($1,000 \leq \text{titer} \leq 10,000$)
 - High (titer >10,000)

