8. STUDY TREATMENTS

8.1. Investigational and Reference Treatments

In Part A, patients will receive 1 dose of evinacumab 15 mg/kg IV infusion over 65 minutes at the baseline visit (day 1).

In Part B, patients will receive evinacumab at a dose assessed from Part A and will be administered IV over a 65-minute infusion Q4W starting at the baseline visit (day 1). The last dose of evinacumab will be at week 20.

In Part C, patients from Part A will initially receive evinacumab at 15 mg/kg IV Q4W. The final dose selection in Part C will be based on data from Part A and data in adults from other studies. Therefore, the dose for patients from Part A entering Part C may be adjusted once the dose selection for Part B is completed.

The IV dose should be prepared using the patient's most recent weight. The most recent weight is either the current visit's weight or, if the current visit's weight is not available when preparing the dose, the weight from the previous visit. Further instructions on dose preparation are provided in the pharmacy manual.

Dosing should fall within a window of ± 7 days; if >14 days have passed, skip the dose and return to the original schedule.

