10.2.4. Infusion Reactions

Infusion reactions are defined as any relevant AE that occurs during the infusion or within 2 hours after the infusion is completed.

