4.8.1.2. Adverse Events of Special Interest

Adverse events of special interest (AESI) are AEs (serious or non-serious) required to be monitored, documented, and managed in a pre-specified manner. AESIs will be recorded on the adverse event e-CRF using dedicated tick boxes, and/or identified using standard MedDRA queries (SMQ), company MedDRA queries (CMQ), MedDRA terms, and/or applicable laboratory assessments. [Appendix 10.3](#) contains the definitions used to identify AESIs:

The AESIs include:

- Anaphylactic reactions (e-CRF)
- General allergic events (SMQ)
- Moderate or severe infusion reactions (e-CRF)
- Hepatic Disorder (SMQ, lab data)
- Pregnancy (e-CRF)
- Symptomatic overdose with investigational medicinal product (e-CRF)
- Neurocognitive events (CMQ)
- New onset of diabetes (NOD) (lab data, HLT, and concomitant medications)
- Pancreatitis (e-CRF)

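### SAP 5.11.3.2 relates ADA and NAb status to injection site reactions in an IV-only study and does not name infusion reactions, the study's own AESI

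*SAP*

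**What the plan says.** SAP 5.11.3.2 sets the scope of the immunogenicity-safety analysis: "Potential association between immunogenicity variables and safety may be explored with a primary focus on the following safety events during the TEAE period". Three events follow: "Injection site reaction (serious or severe and lasting 24 hours or longer", "Hypersensitivity (SMQ: Hypersensitivity [Narrow" and "Anaphylaxis (SMQ: Anaphylaxis [Narrow". The same section then fixes the groups to be used if the analysis is run: ADA positive, ADA negative, persistent response, NAb positive, and maximum titer class.

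Protocol 8.1 gives the route. For Part A: "In Part A, patients will receive 1 dose of evinacumab 15 mg/kg IV infusion over 65 minutes at the baseline visit (day 1". For Part B the drug "will be administered IV over a 65-minute infusion Q4W starting at the baseline visit (day 1". Part C is also IV every four weeks. No part includes an injected dose.

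Protocol 10.2.4 defines the route-specific event: "Infusion reactions are defined as any relevant AE that occurs during the infusion or within 2 hours after the infusion is completed". Protocol 8.5.1 requires every infusion reaction to be reported as an AE and graded, and Protocol 10.2.5 supplies the grading scale. Protocol 10.1.4 makes the moderate and severe grades an AESI, and SAP 4.8.1.2 carries this over as "Moderate or severe infusion reactions (e-CRF". SAP Table 6 identifies infusion reactions by a tick box on the AE page and not by a MedDRA query. SAP 5.8.2 tabulates them by intensity (mild, moderate, severe), events per administration and time to first reaction, with no split by ADA or NAb status.

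**The concern.** A list of focus events should match how the drug is given. Here the only route-specific item is worded for injections, while the route-specific event that the study defines, grades and flags is not named. Protocol 2.2 makes immunogenicity a secondary objective of Part B, and SAP 5.11.3.2 is the only section that sets safety events against ADA and NAb status.

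If the list is programmed as it stands, the tables may have a row with little or nothing to count and none for infusion reactions as such. Adding that row after the data are seen would be open to the criticism that it was data-driven. SAP Section 1 gives pre-specification before database lock as the purpose of the document.

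**Working it through.** No arithmetic applies, because the documents attach no number to this analysis. The check sets the texts side by side.

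1. **Match to route.** Of the three events in SAP 5.11.3.2, hypersensitivity and anaphylaxis do not depend on route. Injection site reaction does, and it does not match Protocol 8.1.

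2. **Where else injection site reactions appear.** Apart from 5.11.3.2, the SAP uses the term only in Table 6, to exclude preferred terms from the general allergic events AESI. Nine terms are listed there under that label: four begin with infusion site (dermatitis, hypersensitivity, rash, urticaria) and five with injection site (the same four plus vasculitis); 4 + 5 = 9. The SAP's own usage can therefore stretch to local reactions at the IV site. Injection site reaction is not an AESI, and no section defines it as an analysis event.

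3. **How infusion reactions are identified.** The protocol defines them by timing: during the infusion or up to 2 hours after it. Table 6 answers no to a MedDRA query for them. Preferred terms are thus not the SAP's method for finding this event, so the two query-based items in 5.11.3.2 overlap with it without replacing it.

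4. **What the present list would catch among timing-defined infusion reactions.**

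| Type of reaction | Examined by ADA/NAb status as written? |
|---|---|
| Coded to a narrow hypersensitivity or anaphylaxis term | Yes |
| Local, at the infusion site, meeting the first item's severity and duration threshold | Only if that item is read with Table 6 |
| Local, at the infusion site, below that threshold | Only if its term lies in a narrow query |
| Any other | No |

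5. **Is the last row realistic?** Protocol 8.5.1.1 lists events that call for interrupting the infusion, among them chills, vomiting and cough. The documents do not give the contents of the narrow queries. I assume that at least some events of this kind are coded outside them. If all were inside, the gap would close; if few were, most infusion reactions would fall in the last row. The documents do not allow a figure between these ends.

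6. **Duration threshold.** Even on the generous reading in step 2, the first item requires at least 24 hours. An acute reaction that settles within hours would not meet it.

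7. **Which grades are flagged.** SAP 4.8.1.2 ties the e-CRF source to moderate or severe reactions, Table 6 says infusion reactions without a grade, and 5.8.2 tabulates mild ones too. The sections do not agree on whether the tick box captures mild reactions.

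**The case against.** The strongest reply is that little is lost. The analysis is optional: the SAP says it may be explored, and Protocol 11.4.7 says only that such an assessment may be provided. A primary focus is not an exhaustive list, so adding infusion reactions would not depart from the SAP. Infusion reactions coded to hypersensitivity or anaphylaxis terms are already covered. With about 6 + 14 = 20 children, ADA titer listings (SAP 5.11.1), the patient listing of TEAEs (Protocol 11.4.5.1) and the narratives required for AESIs (Protocol 10.1.3) would let a reader match cases by hand. During Part B treatment, ADA is sampled only at baseline and week 24, so any cross-table would have very small cells.

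All of this stands, and it limits the weight of the point. It also rules out several stronger readings that a reader might infer:

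- **That the first item is empty by construction.** Table 6 groups infusion-site terms under the same label, so local reactions at the IV site could be counted.
- **That a committed comparison is defective.** The text commits to none.
- **That infusion reactions escape the ADA analysis altogether.** Those coded to the two query-based events do not.
- **That the item was carried over from a subcutaneous study, or that infusion reactions are the event most relevant to ADA.** The documents say neither.

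The objection does not remove the omission itself. If the analysis is run, the list is what will be programmed, and it leaves out infusion reactions coded elsewhere. Matching cases by hand from listings does not replace a pre-specified summary.

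**Conclusion.** The point holds as a small, free improvement. SAP 5.11.3.2 names an event worded for the wrong route and does not name infusion reactions, although the study defines, grades and tabulates them and treats the moderate and severe ones as an AESI. The consequence is that infusion reactions coded outside the narrow hypersensitivity and anaphylaxis terms, and outside any local-site reading of the first item, would not be examined by ADA or NAb status.

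This affects one optional, descriptive paragraph. No efficacy analysis, endpoint or stated conclusion changes, and the primary endpoint is unaffected. The conclusion rests on dosing being IV throughout, which Protocol 8.1 supports, and on the assumption that some infusion reactions are coded outside the two narrow queries, which the documents make plausible but do not quantify. Counts by ADA category will be small whatever is listed.

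**What to change.** In SAP 5.11.3.2:

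- Add a focus event: *Infusion reactions (protocol 10.2.4 definition; any grade as tabulated in SAP 5.8.2, and moderate or severe as the AESI)*.
- If local reactions are still wanted, reword the first item to *infusion site reaction*. Adding the new event is better than replacing the old one, because replacement would drop local reactions.

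Reconcile SAP 4.8.1.2 with Table 6 on which grades the tick box captures. If it captures only moderate and severe reactions, state how mild ones will be identified, for example from AE onset relative to the infusion.

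The cost is a few lines of SAP text and one more row in an exploratory table. No new assessments are needed, because all infusion reactions are already reported as AEs and graded. The SAP is a first version that reflects Protocol Amendment 1 and plans 18 Part B patients (SAP 2.2) against 14 in the current protocol (11.2), so this can go in with that update. If the first database lock has passed, date the addition and label it as made afterwards.

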6. DATA CONVENTIONS

The following analysis conventions will be used in the statistical analysis.

6.1. Definition of Baseline for Efficacy/Safety Variables

Unless otherwise specified, the baseline assessment is programmatically defined as the last available measurement prior to the date of the first study treatment administration, regardless of the study treatment period.

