11. Parent or legal guardian must sign a separate informed consent form (ICF) and patient must sign a separate informed assent prior to collection of Future Biomedical Research samples. Patients are still eligible to enroll in the study if they do not wish to participate in the Future Biomedical Research.
12. Parent or legal guardian must sign a separate informed consent form (ICF) and patient must sign a separate informed assent to participate in the optional genomics sub-study prior to collection of whole blood DNA samples. Patients are still eligible to enroll in the study if they do not wish to participate in the genomics sub-study. One DNA sample for the genomics sub-study should be collected on day 1 (visit 2) but can be collected at any visit after that.

13. Carotid ultrasound imaging will be performed only at sites with this capability. Every effort should be made for patients to undergo 2 carotid ultrasound imaging assessments before the first dose of study drug. The assessments should be separated by at least 1 day.
14. For patients who require stabilization of their background LMT (including apheresis) or need to undergo genotyping to confirm diagnosis of HoFH.
15. Only for patients who do not enter Part C.
16. If continuing to Part C, this visit can occur on the same day as visit 1 of Part C.
17. If the patient requires a run-in, the ICF should be signed at that time; otherwise, the ICF should be signed at the screening visit.

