9.2.6. Ultrasound Imaging

Carotid ultrasound is a reliable method to measure carotid intima-media thickness (cIMT; in mm), which has been shown to be increased in children with HoFH ([Kusters, 2014](#)). The technique has shown reliable results with an interobserver coefficient of variation of 7.3% ([Doyon, 2013](#)).

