4.9. Other Variables

Other assessment endpoints are listed and defined below. Protocol schedule visits will be assigned to the Global Analysis Windows (See [Appendix 10.2](#)).

- The change in hemoglobin A1c (HbA1c [%]) from baseline to post-baseline visits.
- The percent change in hs-CRP from baseline over time.
- The percent change in HDL-C from baseline over time.
- The change in carotid intima-media thickness (cIMT in mm) from baseline over time

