5. STATISTICAL METHODS

In general, patient data collected in Part A will be summarized for all patients (i.e., Part A Total). For Part B, data will be summarized again for all patients (i.e., Part B Total). Part C data summaries will show three columns, specifically, patients treated in Part A, patients treated in Part B, and Total. The baseline value is defined as the last available measurement prior to the date of the first study treatment administration regardless of the study treatment period.

In addition, pooled analyses will summarize data in three columns, specifically, Part A Patients, Part B Patients, and Total. The baseline value for the pooled analyses is defined as the last available measurement prior to the date of the first study treatment administration regardless of the study treatment period. Note: Although Part A patients only contributed data from Part C for the pooled analyses, Part A patient's baseline is defined as Part A baseline for variable derivations.

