10.2. Windows for Analysis Time Points

Below are the definitions for the visit windows programmatically imposed on measures repeatedly collected over the course of the study. These visit windows reflect the study schedule of assessments as described in the protocol.

The visit windows are constructed using ranges applied to the number of days in study (study days) when the measure is collected. Below are the relevant definitions for the analysis visit windows:

1. Study day is defined as the number of days since the first study treatment administration +1. The first study treatment occurs on Study Day 1.
2. Part C study day is defined as the number of days since the first Part C study treatment administration+1
3. Since the protocol specifies that measurements be collected before study treatment is administered on a given day, it is appropriate that baseline include Day 1.

Table 1: Global Analysis Windows for Part A

Visit label	Targeted Study Day	Analysis Window in Study Day
Baseline	1	Measurement obtained closest to first study treatment, while remaining prior to first study treatment
Week 1	8	2 to 11
Week 2	15	12 to 18
Week 3	22	19 to 25
Week 4	29	26 to 35
Week 6	43	36 to 49
Week 8	57	50 to 63
Week 10	71	64 to 77
Week 12	85	78 to 98
Week 16	113	99 to 140
FU- W8	For patients prematurely discontinued Part A: EOT visit study day + 56 days For patients completed Week 16 visit: 169	For patients prematurely discontinued Part A: EOT visit to 84 days after EOT visit For patients completed Week 16 visit: 141 to 196
Study days are calculated from the day of first IMP infusion, the day of first IMP infusion being Day 1.		

Table 2: Global Analysis Windows for Part B

Visit label	Targeted Study Day	Analysis Window in Study Day
Baseline	1	Measurement obtained closest to first study treatment, while remaining prior to first study treatment
Week 1	8	2 to 11
Week 2	15	12 to 21
Week 4	29	22 to 35
Week 6	43	36 to 49
Week 8	57	50 to 70
Week 12	85	71 to 98
Week 16	113	99 to 126
Week 20	141	127 to 154
Week 24	169	155 to 196
FU- W8	For patients prematurely discontinued trt: last study trt + 84 days For patients completed Part B trt period: 225	For patients prematurely discontinued trt: 56 to 97 days after last trt For patients completed Part B trt period: 197 to 238

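### When two pre-dose carotid scans are available, the SAP's baseline uses only the later one, so the exploratory cIMT change carries avoidable measurement error

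*SAP*

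**What the plan says.** **Collection.** The footnotes to the Part A and Part B schedules (Protocol 9.1.1.1 no. 12 and 9.1.1.2 no. 13) say: "Every effort should be made for patients to undergo 2 carotid ultrasound imaging assessments before the first dose of study drug". They add: "The assessments should be separated by at least 1 day". The request is limited: "Carotid ultrasound imaging will be performed only at sites with this capability". The SAP repeats these footnotes in Appendix 10.7. Follow-up scans are single, at Part A week 16, Part B week 24 and Part C weeks 24 and 48.

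**Analysis.** SAP 4.9 lists the variable as "The change in carotid intima-media thickness (cIMT in mm) from baseline over time" and sends it to the Global Analysis Windows. SAP 5.9 summarises it descriptively and plots means with standard errors. Neither section defines a baseline for cIMT.

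**Baseline rules that therefore apply.**
- SAP 6.1: "the baseline assessment is programmatically defined as the last available measurement prior to the date of the first study treatment administration". The sentence opens by allowing exceptions, but none is made for cIMT.
- SAP 5: "The baseline value is defined as the last available measurement prior to the date of the first study treatment administration".
- Appendix 10.2, Tables 1 and 2: "Measurement obtained closest to first study treatment, while remaining prior to first study treatment". Table 5 has the same rule for the pooled data.
- SAP 6.4: where several values fall in one window, one is selected. None is averaged.

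**Measurement error.** Protocol 9.2.6: "The technique has shown reliable results with an interobserver coefficient of variation of 7.3" (per cent).

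**The concern.** The cIMT endpoint is an intra-patient comparison (Protocol 4.1.3) in a study with no control arm, so each child's own baseline is the only reference. Any error in that baseline enters every later change for that child, including Part C and the pooled summaries, because SAP 5 keeps the baseline from before the first dose in the study. The numbers are small: about 6 children in Part A and 14 in Part B, and only those at sites with imaging. A repeat scan is requested from young children, yet when both scans exist no planned analysis uses the earlier one, whether by averaging, as a covariate or in a repeatability summary. What is at stake is the precision of an exploratory summary, at almost no cost to recover.

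**Working it through.** The documents give no sample size, power or precision figure for cIMT, so there is no planned figure to reproduce. The check compares the variance of the change score under the two baseline definitions.

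**Inputs.** Per-scan error SD s = 7.3% of mean cIMT, taken from the interobserver coefficient of variation in Protocol 9.2.6 (using it as per-scan error is an assumption). Part B n = 14 (Protocol 11.2), an upper bound because not every site will image. n = 7 is an assumed smaller number.

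**Step 1: measurement error only, independent between scans.**
- Follow-up minus the last scan: variance = s² + s² = 2s²; SD = √2 × 7.3 = 10.3%.
- Follow-up minus the mean of two scans: variance = s² + s²/2 = 1.5s²; SD = √1.5 × 7.3 = 8.9%.
- SD ratio = √(1.5/2) = 0.866, so the SD is 13% lower. Variance ratio = 0.75, so the variance is 25% lower. Neither ratio depends on the 7.3%.
- A simulation of 1,000,000 patients gave 10.32 and 8.94.

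**Step 2: standard error and 95% half-width (t distribution; the SAP plans no interval for cIMT, so this is only to show scale).**

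| n | SE, last scan | SE, mean of two | Half-width, last scan | Half-width, mean of two |
|---|---|---|---|---|
| 14 | 2.76% | 2.39% | 5.96% | 5.16% |
| 7 | 3.90% | 3.38% | 9.55% | 8.27% |

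Under these assumptions, 14 children with the last-scan baseline give the precision of 14 × 0.75 = 10.5 children with the averaged baseline.

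**Step 3: relax the assumptions one at a time.**

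*True change varies between children with SD d.* Compare √(d² + 2s²) with √(d² + 1.5s²).

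| d | Last scan | Mean of two | SD reduction |
|---|---|---|---|
| 2.5% | 10.62% | 9.28% | 12.6% |
| 5% | 11.47% | 10.24% | 10.7% |
| 10% | 14.37% | 13.41% | 6.7% |

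*The two baseline scans share a fraction r of their error variance; follow-up error is independent.* SD with the mean = s√(1 + (1 + r)/2), against 10.32%.

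| r | Mean of two | SD reduction |
|---|---|---|
| 25% | 9.31% | 9.9% |
| 50% | 9.66% | 6.5% |
| 75% | 10.00% | 3.2% |
| 100% | 10.32% | 0 |

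*Only a fraction p of children have both scans.* Average variance = s²(1 + 0.5p + (1 − p)). At p = 50% this is 1.75s², SD 9.66%, a reduction of 6.5%.

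The direction never reverses in these cases. The gain is zero only if the two scans share all their error or if no child has both.

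**The case against.** **Purpose.** A reader might infer that the second scan was requested in order to be averaged. Neither document says what it is for. A backup for an unusable scan, familiarisation of a young child or a repeatability check would fit the footnote equally well, and under the first two a last-available rule is coherent. This stands: averaging is a better use of the data, not a purpose the protocol states.

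**The earlier scan is not wasted in every case.** It would be too strong to say that it is collected and never used. Under a last-available rule it becomes the baseline if the later scan is missing or unusable. The point is confined to children with both scans available.

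**The size.** The 7.3% is an interobserver figure, and nothing says that different observers perform a child's scans. If one observer does both baseline scans, part of the error may be shared and averaging will not remove it. If the same observer also does the follow-up, that part largely cancels from the change, and both 10.3% and 8.9% are too high. This stands: 13% is a ceiling and the absolute figures are illustrative.

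**Coverage.** Two scans are sought on a best-effort basis at capable sites only. The documents do not say how many children will be imaged, let alone imaged twice.

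**The heading of SAP 6.1** names efficacy and safety variables, whereas cIMT is listed under other variables. This does not rescue the plan, because SAP 5 and Appendix 10.2 impose the same single-value rule.

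**Importance.** The lack of a control arm limits interpretation of cIMT far more than baseline error does, and averaging does nothing for that.

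**Conclusion.** The point holds as a minor, nearly free improvement. As written, the SAP leaves the earlier pre-dose scan out of the cIMT change from baseline whenever both scans are available, so the summary carries more measurement error than the requested data require. The 13% reduction in SD (25% in variance) applies only if scan errors are independent, measurement error dominates and every imaged child has both scans. Under the less favourable single-assumption cases above it is about 3 to 10%. Follow-up scans remain single, so even at best only a quarter of the error variance is removed. The gap in the baseline rules is certain; the size of the gain is not. The analysis is exploratory and descriptive, and no primary, secondary or safety result is affected.

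**What to change.** Add to SAP 4.9: *For cIMT, notwithstanding Sections 5, 6.1, 6.4 and Appendix 10.2, baseline is the mean of all valid pre-dose assessments; if only one is available, that value is used.* The override must be explicit, because a bare sentence in 4.9 would conflict with SAP 5 and with Tables 1, 2 and 5 of Appendix 10.2.

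Apply the definition to the Part A, Part B, Part C and pooled cIMT summaries and plots. Report how many children contribute one baseline scan and how many contribute two, since their baselines differ in precision. Settle before database lock what counts as a valid pre-dose scan, including whether one taken early in the run-in (which can start at day −70) qualifies. A short repeatability summary of the paired scans would be a useful addition, giving the study its own error estimate in place of the cited interobserver figure. If the second scan has some other purpose, the SAP should say so.

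The cost is a sentence in the SAP, a small programming change and one extra line in a table. No new scans, visits or patients are needed.
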